10.1. Population of Interest

The exploratory analyses will be based on the PKPD population, unless otherwise specified.

12. APPENDICES

12.1. Appendix 1: Schedule of Activities

12.1.1. Protocol Defined Schedule of Events

Table 9 Schedule of Activities

Visit Study Day	Baseline (includes a screening window of up to 24 hours before the first dose of study treatment)		On-Therapy					Test-of-Cure 10 to 13	Follow-up 28±3
	-1	1		2	3	4	5 ^a		
Procedure		Predose	Postdose						
Written informed consent	X								
Inclusion and exclusion criteria	X								
Admission to clinic	X								
Participant demography	X								
Physical examination (including height and weight at Baseline only)	X						X	X	
Medical/surgical history	X								
Diagnosis of presumptive acute cystitis ^b	X								
Bacteriology samples ^c		X		X	X	X	X	X	X
Record acute cystitis signs and symptoms ^d	X			X	X	X	X	X	X
12-lead ECG ^e	X	X ^f	X			X			
Vital sign measurements ^g	X	X ^f		X	X	X	X	X	
Hematology, chemistry, and urinalysis	X				X		X	X	
Serology (hepatitis B and C and HIV) ^h	X								
Pregnancy test ⁱ	X						X	X	
Administer study treatment ^j			X ^j	X	X	X	X ^j		
Blood and urine PK sampling ^k		X	X	X	X	X	X		
Cervical, rectal, and pharyngeal PK sampling (optional) ^l						X			
Genetic sample (optional)		X ^m							
Stool microbiome collection (optional) ⁿ		X					X		X
Vaginal and pharyngeal microbiome collection (optional) ⁿ		X					X		X

Visit	Baseline (includes a screening window of up to 24 hours before the first dose of study treatment)		On-Therapy					Test-of-Cure	Follow-up
Serious adverse events ^{o,p}	X	X	X	X	X	X	X	X	X
Adverse events ^p			X	X	X	X	X	X	X
Concomitant medications	X	X	X	X	X	X	X	X	X
Discharge from clinic							X ^{a,j}		
Schedule/Reminder for next outpatient visit							X ^q	X ^r	X ^r

ECG=electrocardiogram; HIV=human immunodeficiency virus; PK=pharmacokinetic; TOC=Test-of-Cure; WBC=white blood cell.

- a. If a participant discontinues during the on-treatment confinement period, Day 5 assessments will be completed before the participant is discharged, with the exception of study treatment administration.
- b. Based on confirmation of pyuria (≥ 10 WBC/mm³ or the presence of leukocyte esterase) and/or nitrite from a pretreatment clean-catch midstream urine sample per local laboratory procedures. Note: Repeat baseline urine samples are allowed if contamination, defined as ≥ 10 squamous epithelial cells, is observed under microscopic evaluation.
- c. Participants will provide a clean-catch midstream urine sample pretreatment at Baseline (predose on Day 1), predose on Days 2 through 5 (i.e., before the time-matched dose); and at the TOC and Follow-up Visits for Gram stain, quantitative bacteriology culture, and in vitro antimicrobial susceptibility testing.
- d. Site staff will record clinical signs and symptoms of acute cystitis based on participant interview.
- e. Obtain a triplicate 12-lead ECG in semi-supine position at Baseline only. See Table 10 for single 12-lead ECG predose and postdose assessment time points on Days 1 and 4.
- f. Only repeat the ECG and vital sign assessments at predose on Day 1 if the baseline assessment was not within 4 hours of the first dose of study treatment.
- g. Take measurement of temperature, blood pressure, and pulse rate in semi-supine position.
- h. If serology testing was performed within 3 months prior to the first dose of study treatment and results were positive, testing at Baseline is not required. If testing was performed within 3 months and any result was negative, testing at Baseline is required.
- i. For women of childbearing potential, a negative serum pregnancy test is needed for eligibility at Baseline. A urine pregnancy test may be performed on Day 5 and at the TOC Visit.
- j. The first dose on Day 1 will only be administered after all baseline procedures have been completed. All doses of study treatment will be administered under site staff supervision and all doses will be administered with food (i.e., standardized meals or snacks as applicable). Participants should remain in the clinic to complete a total of 10 doses.
- k. See Table 10 for serial collection time points. Predose PK blood samples will be collected before each time-matched dose on Days 1 through 5. Predose PK urine samples will be collected 0 to 2 hours before each time-matched dose on Days 1 through 5. Only 1 sample is needed when serial and predose samples overlap. If a participant is switched to a different antibiotic before the end of study treatment, a final blood and urine PK sample should be collected prior to administration of the different antibiotic.
- l. Collection of cervical, rectal, and pharyngeal swab PK specimens is optional. Specimens will be collected on Day 4 at predose and at approximately 2 hours postdose. The 2-hour postdose collection should be as close as possible to the 2-hour postdose blood PK draw time on Day 4.
- m. Collect sample only if the participant has a signed consent specific for this purpose. Baseline (predose on Day 1) is the recommended time to collect the sample, but it can be collected at any time during the study.
- n. Collection of stool, vaginal, and pharyngeal microbiome specimens is optional. The pretreatment specimens may be collected any time from Day -1 to Day 1 predose. The posttreatment specimens on Day 5 and at Follow-up may be collected at any time. Posttreatment stool, vaginal, and pharyngeal microbiome specimens should only be collected from participants who had a corresponding baseline specimen collected for each specimen type.
- o. Record serious adverse events from the time of consent.

- p. Record adverse events from the time of the first dose of study treatment.
- q. Confirm return day/time for the TOC and Follow-up Visits.
- r. Pre-visit reminder: Site staff will contact the participant 24±4 hours before the scheduled TOC and Follow-up Visits.

Note:

At the discretion of the investigator, for emergency purposes only, participants may temporarily leave the clinic on study days without serial PK collections and only at times that do not interfere with required study assessments. Participants will be instructed to follow the protocol restrictions. The investigator will ensure the participant is eligible to continue in the study upon return to the clinic. All doses of study treatment will be administered under site staff supervision in the clinic.

The timing and number of planned study assessments, including PK assessments may be altered during the study based on newly available data (e.g., to obtain data closer to the time of peak plasma concentrations) to ensure appropriate monitoring. Any changes in the timing or addition of time points for any planned study assessments must be documented and approved by the relevant study team member and then archived in the sponsor and site study files, but will not constitute a protocol amendment. The institutional review board will be informed of any safety issues that require alteration of the safety monitoring scheme or amendment of the informed consent form.

Table 10 Blood and Urine Pharmacokinetic Collections and Electrocardiogram Assessments on Days 1 and 4

Procedure ^a	Time point (hours)											
	Predose	0	0.5	1	1.5	2	3	4	6	8	10	12
12-lead electrocardiogram ^b	X ^c					X						
Administer study treatment ^d		X										X ^e
Blood collection for pharmacokinetics ^f	X		X	X	X	X	X	X	X	X		X
Urine collection for pharmacokinetics ^g	X	X				X		X	X	X	X	

- Assessments scheduled at the same nominal time should occur in the following order: electrocardiogram, urine collection, blood collection. The timing of the assessments should allow the blood draw to occur at the exact nominal time.
- Obtain single 12-lead electrocardiogram in semi-supine position at predose and 2 hours postdose on Days 1 and 4. The predose and postdose electrocardiogram time points should be the same on both days.
- Only repeat the electrocardiogram assessment at predose on Day 1 if it was not performed within 4 hours of the baseline assessment.
- Study treatment will be administered under site staff supervision and with food (i.e., standardized meals or snacks as applicable). On Days 1 and 4, for the dose associated with serial PK collections, participants should be in a semi-supine position for approximately 3 hours after study treatment administration with only minor exceptions (e.g., urine PK collections).
- Collection of the PK samples should occur before this dose is administered.
- Blood PK samples will be collected at predose and 0.5, 1, 1.5, 2, 3, 4, 6, 8, and 12 hours postdose for the first dose of study treatment on Day 1 and for the time-matched dose on Day 4.
- Urine PK samples will be collected predose and at intervals of 0 to 2 hours, 2 to 4 hours, 4 to 6 hours, 6 to 8 hours, 8 to 10 hours, and 10 to 12 hours postdose for the first dose of study treatment on Day 1 and for the time-matched dose on Day 4.

12.2. Appendix 2: Study Phases and Treatment Emergent Adverse Events

12.2.1. Study Phases

Assessments and events will be classified according to the time of occurrence relative to the start and end date of study treatment.

Study Phase	Definition
Pre-Treatment	Date and Time \leq Study Treatment Start Date and Time
On-Treatment	Study Treatment Start Date and Time $<$ Date and Time \leq Study Treatment Stop Date and Time
Post-Treatment	Date and Time $>$ Study Treatment Stop Date and Time

12.2.1.1. Study Phases for Concomitant Medication

Study Phase	Definition
Prior	If medication end date is not missing and is before participant enrollment
Concomitant	Any medication that is not a prior

NOTES:

- Please refer to [Appendix 5: Reporting Standards for Missing Data](#) for handling of missing and partial dates for concomitant medication. Use the rules in this table if concomitant medication date is completely missing.

12.2.2. Treatment Emergent Flag for Adverse Events

Flag	Definition
Treatment Emergent	
 If AE onset date is on or after treatment start date & on or before the treatment stop date + 2 days. Study Treatment Start Date \leq AE Start Date \leq Study Treatment Stop Date + 2 days.

NOTES:

- Time of study treatment dosing and start/stop time of AEs should be considered, if collected.

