
Gastrointestinal Effects
 
Based on nonclinical data, gastrointestinal effects were mild ulceration of the nonglandular mucosa and minimal erosion and/or mural inflammation of the glandular mucosa in stomach (rat, oral study); moderate cecal ulceration and minimal colonic erosion (rat, IV study); and vomiting (dog).
 
Lower gastrointestinal effects (soft stools, flatulence, and diarrhea) are among the most common AEs reported in gepotidacin clinical studies.
	
Gastrointestinal effects observed in gepotidacin clinical studies, both Phase I studies and the Phase II ABSSSI study, included diarrhea (very common, $\geq 10\%$) and flatulence (common; $\geq 1\%$ and $< 10\%$); all nonserious and mild in severity (see Section 6 of the IB).
 
In the Phase II urogenital gonorrhea study, the most frequently reported gastrointestinal AEs overall were diarrhea, flatulence, abdominal pain, and nausea. Comparing the treatment groups, the incidence of diarrhea and nausea was higher in the 3000-mg treatment group and incidence of flatulence was higher in the 1500-mg treatment group.
 
Few occurrences of Clostridium difficile have been reported in clinical studies (see Section 6 of the IB). Of the 357 healthy participants in Phase I studies who have received gepotidacin, C. difficile was reported in 8 participants, including 2 elderly participants in association with soft stools or diarrhea. No participants in the Phase II ABSSSI or Phase II urogenital gonorrhea study received a diagnosis of C. difficile-associated diarrhea.
	
See Section 6.2 for excluded medical conditions. Close monitoring of clinical parameters and AEs (Table 1) will be conducted to mitigate and assess gastrointestinal effects. Suspected C. difficile infection will be managed according to a prespecified algorithm provided in the Study Reference Manual.

Potential Risk of Clinical Significance	Summary of Data/Rationale for Risk	Mitigation Strategy

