- On Day 5, vaginal and pharyngeal swab microbiome specimens will be obtained from participants who consent to provide such specimens.
- On Day 5, after all study procedures have been performed, including a predose clean-catch midstream urine sample for Gram stain, quantitative bacteriology culture, and antimicrobial susceptibility testing, predose PK sample collections, and safety assessments, participants will be discharged from the clinic. Participants should remain in the clinic to complete a total of 10 doses. Participants will be instructed to return for the TOC (Day 10 to 13) and Follow-up (Day 28±3) Visits.

- At any time during the study, participants experiencing new or continuing signs and symptoms of acute cystitis will be assessed and treated per the investigator's judgement. If a participant is switched to a different antibiotic before or during the TOC Visit, all TOC procedures should be completed before the other antibiotic is started. Any participant who discontinues from the PK portion of the study should return for the TOC and Follow-up Visits.

Outpatient Visits

- **TOC (Day 10 to 13) Visit:** Participants will return for the TOC Visit 5 to 8 days after completion of study treatment. Clinical signs and symptoms of acute cystitis will be recorded ([Appendix 10](#)) and samples for Gram stain, quantitative bacteriology culture, and antimicrobial susceptibility testing will be collected. Safety assessments will be performed and AEs and concomitant medication use will be recorded.
- **Follow-up (Day 28) Visit:** Participants will return for the Follow-up Visit 28 (± 3) days after the start of study treatment. Clinical signs and symptoms of acute cystitis will be recorded ([Appendix 10](#)) and samples for Gram stain, quantitative bacteriology culture, and antimicrobial susceptibility testing will be collected. Adverse events and concomitant medication use will be recorded. A stool microbiome specimen will be obtained from participants who consent to provide such specimens. Vaginal and pharyngeal swab microbiome specimens will be obtained from participants who consent to provide such specimens.

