9.2.1. Time Period and Frequency for Collecting AE and SAE Information

- All SAEs will be collected from the signing of the ICF until the Follow-up Visit at the time points specified in [Table 1](#).
- All AEs will be collected from the start of treatment until the Follow-up Visit at the time points specified in [Table 1](#).
- Medical occurrences that begin before the start of study treatment but after obtaining informed consent will be recorded on the Medical History/Current Medical Conditions section of the eCRF not the AE section.

- All SAEs will be recorded and reported to the sponsor or designee immediately and under no circumstance should this exceed 24 hours, as indicated in [Appendix 4](#). The investigator will submit any updated SAE data to the sponsor within 24 hours of it being available.
- Investigators are not obligated to actively seek AEs or SAEs in former study participants. However, if the investigator learns of any SAE, including a death, at any time after a participant has been discharged from the study, and he/she considers the event to be reasonably related to the study treatment or study participation, the investigator must promptly notify the sponsor.
- The method of recording, evaluating, and assessing causality of AEs and SAEs and the procedures for completing and transmitting SAE reports are provided in [Appendix 4](#).

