9.3. Treatment of Overdose

There is no specific antidote for overdose with a bacterial topoisomerase inhibitor. In the event of a suspected overdose, it is recommended that the appropriate supportive clinical care should be instituted, as dictated by the participant's clinical status.

In the event of an overdose, the investigator should:

1. Contact the medical monitor immediately.
2. Closely monitor the participant for AEs/SAEs and laboratory abnormalities until study treatment can no longer be detected systemically (at least 72 hours).
3. Obtain a plasma sample for PK analysis within 24 hours from the date of the last dose of study treatment if requested by the medical monitor (determined on a case-by-case basis).

4. Document the quantity of the excess dose as well as the duration of the overdosing in the eCRF.

Decisions regarding dose interruptions or modifications will be made by the investigator in consultation with the medical monitor based on the clinical evaluation of the participant.

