12.5.2.1. Handling of Missing and Partial Dates

Element	Reporting Detail
General	
 Partial dates will be displayed as captured in subject listing displays.
Adverse Events	
 The eCRF allows for the possibility of partial dates (i.e., only month and year) to be recorded for AE start and end dates; that is, the day of the month may be missing. In such a case, the following conventions will be applied for calculating the time to onset and the duration of the event: 
 Missing Start Day: First of the month will be used unless this is before the start date of study treatment; in this case the study treatment start date will be used and hence the event is considered On-treatment as per Appendix 3: Study Phases and Treatment Emergent Adverse Events. Missing Stop Day: Last day of the month will be used, unless this is after the stop date of study treatment; in this case the study treatment stop date will be used. Completely missing start or end dates will remain missing, with no imputation applied. Consequently, time to onset and duration of such events will be missing. Adverse events with entirely missing or unknown start dates will be assumed to be on-treatment for reporting.
Concomitant Medications/	
 Partial dates for any concomitant medications recorded in the CRF will be imputed using the following convention:

Element	Reporting Detail
Medical History	

○ If the partial date is a start date, a '01' will be used for the day and 'Jan' will be used for the month
○ If the partial date is a stop date, a '28/29/30/31' will be used for the day (dependent on the month and year) and 'Dec' will be used for the month.
● The recorded partial date will be displayed in listings.

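### The SAP's rule for a missing AE stop day can put the stop date before the start date; separately, the treatment-emergent flag closes 2 days after the last dose and the SAP does not say which AE tables use it

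*SAP*

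**What the plan says.** **Partial stop dates.** SAP 12.5.2.1 covers AEs with a missing day of the month and says the imputed dates feed time to onset and duration. A missing stop day becomes the last day of the month, "unless this is after the stop date of study treatment; in this case the study treatment stop date will be used". The rule does not refer to the AE's own start date.

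**Flag.** SAP 12.2.2 calls an AE treatment-emergent if its onset is on or after treatment start and "on or before the treatment stop date + 2 days". Clock times are to be considered if they were collected.

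**Collection.** Protocol 9.2.1 states: "All AEs will be collected from the start of treatment until the Follow-up Visit". Protocol section 9 places that visit at Day 28 ± 3. For Test-of-Cure (TOC, Day 10 to 13) it says "Participants will return for the TOC Visit 5 to 8 days after completion of study treatment".

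**Endpoint and displays.** The safety endpoint in SAP 2.2 is treatment-emergent AEs and SAEs, plus change from baseline in vital signs, ECGs and laboratory tests. Protocol 10.3.2 promises the number and percentage of treatment-emergent AEs. SAP 8.1 and Tables 3.1–3.3 refer simply to adverse events, with no treatment-emergent restriction. Listings 18–22 cover all AEs, related AEs, SAEs and AEs leading to discontinuation or withdrawal.

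**The concern.** Dosing lasts about 5 days and AE follow-up about 4 weeks. A rule that pulls a late stop date back to the last dose suits a study in which follow-up ends soon after treatment. Here most of the follow-up comes after treatment, so the cap will often apply when a stop day is missing, and nothing prevents an impossible result.

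The flag is a separate matter because it uses onset date only. The endpoint is worded in terms of treatment-emergent AEs, yet the only definition of that term closes before the first outpatient visit. The protocol does not define the term, neither document explains the 2 days, and SAP 2.1 (changes to the protocol analysis) does not mention it. Two programmers working from this SAP could produce different versions of Tables 3.1–3.3. With 25 to 30 participants, one participant is 3.3–4.0% (1/30 to 1/25), and Table 3.3 applies a 5% cut. If the flag governed that table, removing one of two affected participants would take a term from 6.7–8.0% (2/30 to 2/25) to 3.3–4.0%, and the term would disappear.

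**Working it through.** **1. Day of the last dose.** Protocol 7.1 gives 10 doses about 12 hours apart, the first by 2 PM on Day 1.
- Last dose = first dose + 9 × 12 h = + 108 h, or 4.5 days.
- First dose before noon: last dose on Day 5. Then 5 + 5 = 10 and 5 + 8 = 13, which reproduces the protocol's TOC window of Day 10 to 13.
- First dose from noon to 2 PM: last dose early on Day 6, with TOC 4 to 7 days later.

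**2. Stop-date rule.** Let L be the last-dose date, S a known AE start date with S > L, and M the end of the recorded stop month.
- The AE cannot stop before it starts, so M ≥ S > L.
- M is therefore always later than L, the cap always applies, and the imputed stop is L, which is before S.

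The error is thus certain for this class of AE. As a check, the rule was applied to every first-dose date in a 365-day year, last dose on Day 5 or 6, onset on Days 1 to 28, and assumed true durations of 0, 1, 3, 7 and 14 days. The stop preceded the start in 100% of cases with onset after the last-dose date and in 0% with onset on or before it.

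Examples, with dosing 6 to 10 March:

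| AE onset | Stop recorded | Imputed stop | Stop − start |
|---|---|---|---|
| 15 March | March | 10 March | −5 days |
| 11 March (inside the flag window) | March | 10 March | −1 day |
| 8 March, truly resolved 20 March (assumed) | March | 10 March | 2 days instead of 12 |

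The SAP gives no duration formula. Counting both end days adds 1 to each figure.

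**3. Flag window against collection.**
- Window end = last-dose day + 2 = Day 7 or Day 8. Using clock times does not carry it past Day 8.
- Share of calendar days outside, Follow-up on Day 28: (28 − 7)/28 = 75.0%, or (28 − 8)/28 = 71.4%.
- Extremes over Day 25 to 31: (25 − 8)/25 = 68.0% and (31 − 7)/31 = 77.4%.
- TOC starts on Day 10, after Day 8. After a full course, an AE with a complete onset date at TOC or later cannot be treatment-emergent.

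**4. Missing start days work the other way.** A missing start day becomes the first of the month, or treatment start if that is later. Over the same 365 first-dose dates, with last dose on Day 5, about 64% of true onsets on Days 8 to 28 would be moved to Day 7 or earlier if the start day were missing. A late AE with a vague onset date can therefore be flagged when the same AE with a full date is not.

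**The case against.** The strongest reply is that nothing is shown to be lost. The SAP never says its AE tables are restricted by the flag. As titled, Tables 3.1–3.3 would include an AE on Day 12, and the listings keep every AE. SAEs are not clearly limited by the flag and are all listed. Laboratory and vital-sign abnormalities at TOC also reach the change-from-baseline tables (3.4, 3.5, 3.12), the worst-case vital-signs table (3.11) and the Grade 2 or higher listings, none of which depends on the flag. Physical examination, vital signs and laboratory tests are also scheduled on Day 5, inside the window. All of this stands. It leaves an unresolved mismatch: if the tables use the flag, late non-serious AEs leave the incidence summaries; if they do not, no planned table is identified as reporting the endpoint as worded. The sponsor standards cited in SAP 8.1 may settle this, but the SAP does not say so.

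On stop dates, duration is neither an endpoint nor the subject of any titled table, listings show partial dates as captured, and a study this size may have no such case. That limits the effect but does not make the rule correct.

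A reader might infer more from three places:
- **Systemic drug at 72 hours.** The text in Protocol 9.3 is an instruction for monitoring a suspected overdose. It says nothing about drug levels after the planned regimen.
- ***C. difficile*.** Protocol 3.3.1 says that, among 357 healthy Phase I participants, it "was reported in 8 participants, including 2 elderly participants in association with soft stools or diarrhea", but gives no onset times. The results also have their own listing (Listing 31).
- **Missing relationship.** One bullet of SAP 12.4.3 limits imputation as related to treatment-emergent AEs. A later bullet treats AEs with missing relationship as related in summary tables without that limit. The text is ambiguous, so it does not show that only flagged events are covered.

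**Conclusion.** The stop-date rule is wrong as written. For every AE with a known onset after the last-dose date and a missing stop day, it gives a stop before the start, and it shortens continuing on-treatment AEs to the last dose. The effect is confined to AE duration; it neither changes the flag nor removes any event. How many AEs would be affected is unknown and could be none.

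The flag is the smaller point. It closes on Day 7 or 8 without stated justification, while the endpoint is treatment-emergent AEs and collection runs to Follow-up. It would be tempting to conclude that most of the AE collection is lost to the safety endpoint, but the documents do not support that. The 71–75% is a share of calendar days with Follow-up on Day 28, no AE timing is given, and the SAP does not apply the flag to any AE table. What is established is that endpoint, flag and displays are not tied together. The day counts assume a full course at about 12-hour intervals; early discontinuation closes the window sooner. The best window length is partly a matter of preference.

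**What to change.** 1. **SAP 12.5.2.1.** Impute a missing stop day as the earlier of the last day of the recorded month and the participant's last study contact, and never before the AE start date. In the March example, with Follow-up on Day 28 (2 April), the 15 March AE would stop on 31 March, a difference of 16 days. The cost is one sentence and a small programming change.
2. **SAP 8.1, 12.2.2 and Tables 3.1–3.3.** State that the AE incidence tables cover onset from first dose through the Follow-up Visit, and show onset up to last dose + 2 days as a breakdown. The cost is a few sentences and the flag programming. The downside is that some late AEs unrelated to the drug, including any that follow another antibiotic, will enter the tables; the breakdown and the drug-related table help the reader to separate them.

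Both changes should be made before database freeze. Neither needs new data.
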